1.1 Nociception and Health

The International Association for the Study of Pain defines pain as an unpleasant sensory and emotional experience associated with actual or potential tissue damage, partially related to the magnitude of the nociceptive signal (1).

Important reductions in nociception are often observed after 8 to 12 weeks of exercise (2); however, as little as 1 session of exercise can induce hypoalgesia (3, 4). This phenomenon is known as exercise-induced hypoalgesia (EIH), a generalized decrease in nociception sensitivity that occurs during exercise and for a short time afterwards (<30 min), relevant in minimizing symptoms in persons with chronic pain (5). Nociception has been quantified in a variety of ways in studies of EIH, with quantitative sensory testing most often used. Quantitative sensory testing describes a series of tests that measure the perceptual responses to systematically applied sensory stimuli (usually pressure, thermal, or electrical) (6). These tests typically involve the quantification of the individual nociceptive threshold and tolerance, which are, respectively, the minimum intensity of a stimulus that is perceived as painful and the maximum intensity to a noxious stimulus that the participant is willing to tolerate (7). These measures are frequently assessed in the immediate post-exercise period (e.g., 0–15 minutes after exercise termination).

The magnitude of EIH appears to vary according to the combination of volume and intensity of exercise (8, 9, 10), the type of noxious stimulus used (3), the method used to quantify nociception (e.g. threshold, tolerance, rating) (3), the site (e.g. over an exercised or non-exercised muscles) (11, 12, 13), and the timing of nociception assessment (e.g. during or following exercise) (14, 15, 16). Analgesic effects are most common seen when noxious mechanical stimuli are used rather than thermal (17) and its effects are more pronounced in local than in remote muscles (12). While aerobic and isometric resistance exercise have been extensively investigated and its analgesic effect are relative unequivocal, dynamic

resistance exercise has been far less studied (18). In addition, to our knowledge, only one study verified the hypoalgesic effect of a 30s Wingate anaerobic exercise (19).

The most commonly proposed mechanism of EIH relies on enhanced descending inhibition by activation of the opioid and cannabinoid systems (5, 18, 20). The contraction of skeletal muscle increases the discharge of mechanosensitive afferents (i.e., A-delta and C fibers) which, in turn, activate central descending opioid analgesic pathways (21, 22). Exercise also increases the release of endogenous cannabinoids (23). The endocannabinoid system is a neuromodulatory system composed of cannabinoid receptors (CB1, CB2), their endogenous ligands, that is, the endocannabinoids (Narachidonyl ethanolamine [AEA] and 2-arachidonoylglycerol [2-AG]), and proteins responsible for their metabolism (24). The presence of cannabinoid receptors in nociceptive-processing areas of the brain and spinal cord suggests that endocannabinoids contribute to the control of pain through the activation of CB1 receptors (24). The circulating levels of endocannabinoids increase after isometric exercise (23). These opioid and cannabinoids pathways have receptors not only throughout the central nervous systems but also at the periphery and can produce analgesia when stimulated (18). Furthermore, there is evidence of an interplay between the endocannabinoid and opioid systems, such that the activation of one system is mediated by the other system (25).

Exercise-induced changes in the cardiovascular system have also been proposed as a mechanism of EIH (18). Exercise causes an increase in blood pressure which results in the activation of baroreceptors, innervated by vagal afferents, that are synaptically connected to pain modulatory brain areas, associated with blood pressure control, that decrease pain sensibility when activated (26, 27). This network is thought to be composed of interconnected areas including the insular and prefrontal cortices, the amygdala, the hypothalamus, the periaqueductal gray, the nucleus tractus solitarius. However, there's still little evidence to support this (28, 29), once acute increases in blood pressure by exercise could not account for the persistence of EIH after exercise (i.e. 15 min after exercise

cessation blood pressure would have presumably returned to baseline values, or indeed be lower) (18).

The influence of exercise on reducing the sensitivity of the central nervous system has also been explored as a mechanism of EIH (18). There is evidence that acute exercise can reduce temporal summation (30, 31). Very few studies in humans have permitted description of the sites in the central nervous system from which EIH arises. Non-invasive neurophysiological techniques, using functional magnetic resonance imaging (FMRI) and electroencephalographic (EEG) event related potentials (ERP), can provide some insights (18). Ellingson et al., (2016) (32), with FMRI, found that cycling activated brain areas, like the left dorsolateral prefrontal lobe of the anterior insula, that are involved in descending pain pathways inhibition, decreasing pain sensitivity. More recently, Zheng et al. (2021) (33) and Wu et al. (2022) (34), using heat-evoked brain responses, provided evidence that cycling at 70% of heart rate reserve for 20 min and elbow flexor isometric contraction at 40% MVC for 3min, respectively, induced the reduction of N2-P2 peak-to-peak amplitudes (time domain) as well as enhanced alpha oscillation power (frequency domain) in both exercised and non-exercised limbs (corroborated by pressure and heat pain thresholds increases in local and distal muscles). The N2-P2 potentials mainly originates from the anterior and medial cingulate gyrus and reflect the cognitive and emotional processing of pain perception; it's amplitude reveals subject's pain perception. Alpha oscillation power reflects the activation of the resting state sensory-motor neural network and reflects the central descending inhibitory function. Therefore, attending the global EIH effect, the authors concluded that it could be related not only to the modulation of nociceptive information transmission via spinal gate mechanism but also rely on a top-down descending pain inhibitory mechanism.

Additionally, several studies in healthy individuals have found a positive association between EIH and the magnitude of conditioned pain modulation (CPM) (i.e. the paradigm of pain inhibits pain) (35) which is known for evaluating the efficiency of descending pain pathways inhibition, involving both serotonergic and opioidergic mechanisms (5).

However, Ellingson et al. 2014 (36) showed that CPM is only a minor contributor to EIH due to differences in temporal and spatial manifestations. In fact, a significant CPM effect was observed only during evoked pain procedures (i.e. pressure), whereas EIH occurred following exercise. Also, during CPM a significantly larger effect on pressure thresholds was found at the remote sites compared to local sites, whereas EIH was significantly larger in the exercising body part compared to remote sites (13). Therefore, local and segmental mechanisms appear to play important roles for EIH.

Thus, the influence of exercise on reducing peripheral nociceptive sensitivity has also been explored as a mechanism of EIH (18). Preliminary data has provided indirect evidence that the hypoalgesic effect induced by exercise could be possible related to the modulation of the signal transmission via A-delta and C fibers. Using electroencephalographic evoked potentials, Jones et al. (2016) (11) verify that somatosensory-evoked potentials (SEPs) to noxious electrical stimuli delivered to the index finger were unchanged after elbow flexion isometric exercise at 40% MVC for 3 min, whereas laser-evoked potentials (LEPs) to noxious heat delivered to hand dorsum decreased after exercise. This result suggests that the peripheral nociceptor might be involved in EIH in humans, because laser heat stimuli activate peripheral afferents and electrical stimuli bypass the receptors by activating the axons of the nociceptive afferents (11). This was further corroborated by Jones et al. (2017) (37) where by blocking blood flow to an unexercised limb during cycling exercise, resulting in unchanged pressure pain threshold afterwards, provided evidence that factors that are released into the blood during exercise (opioids, cannabinoids, catecholamines), which interact with specific receptors, are able to inhibit the nociceptive signal and therefore modify input before reaching the central nervous system. Nevertheless, the effect of acute exercise on LEPs amplitude attenuation observed by Jones et al., (2016) (11) was not statistical different from the passive rest control condition. The approximately 230ms onset latency of LEP was only compatible with conductive velocity of fast myelinated A delta fibers. The augmented pressure pain threshold verified after exercise resulted from an assessment obtained over a period of

seconds eliciting a sensation of gradually increasing pain, only compatible with the activity of non-myelinated C fibers, which were not directly measured by EEG. Thus, if exercise has greater effects on C compared to A delta fibers further investigation should be addressed on the desensitization role of both afferent fibers post exercise.

On the other hand, the effects of long-term training on nociception have been poorly investigated (18). To our knowledge, only three studies examined nociceptive modulation after exercise training in healthy individuals. Jones et al. (2014) (38) observed increases in ischemic pain tolerance in non-exercising region (upper limb), but not in pain threshold, after cycling training for 30 minutes at 75% of $VO_{2\text{max}}$ 3 times/week for 6 weeks. Recently, in an attempt to establish intensity-dependent effects, O’Leary et al. (2017) (39) observed that 3 times/week for 6 weeks of high intensity cycling interval training but not volume-matched moderate intensity continuous training increased ischemic pain tolerance in the upper limb. On the opposite, Hakansson et al. (2018) (40), in pain-free overweight individuals, only observed augmented pressure pain threshold over the exercised muscles after 6 weeks of moderate-intensity continuous cycling training and not after volume-matched high intensity training.

It is important to mention that none of the above studies tried to establish mechanisms underneath training-induced analgesic effects. Some reports indicate that exercise training decreases cardiovascular sympathetic modulation mainly via central command (41). However, it has also been proposed that training modulates the exercise pressor reflex at cardiovascular level by attenuating the peripheric discharge of group III and IV muscle afferents in response to noxious, metabolic and mechanical stimuli, and thus regulating the sensation of nociception. Sinoway et al. (1996) (42) reported that 4 weeks of forearm training reduce sympathetic responses and mean arterial pressure during rhythmic voluntary handgrip. In addition, there is compelling evidence that endurance-trained individuals have a lower exercise pressor response compared to untrained people (43, 44). Thus, the available data indicate some level of adaptation within the exercise pressor reflex gain following low-resistance high-repetition muscle training, and this is in accordance with

the findings of Somers et al. (1992) (45).

1.2 Analgesia and Performance

The mechanisms underlying neural changes in response to specific experimental interventions can be investigated by measuring reflex responses, namely the H reflex and V wave (46). Despite both responses are under the influence of common neural mechanisms, H-reflex is more sensitive to changes in the intrinsic motoneuron properties and presynaptic inhibition (46, 47, 48), while the V-wave is more sensitive to modifications in supraspinal input to the motoneuron pool (49, 50). In addition, they are task and training dependent (51, 52, 53). Longitudinal studies have revealed positive changes in H-reflex after endurance (52) and Wingate-based training (53), which reflects improvements in spinal excitability. Resistance training has been shown to increase V-wave amplitude (51, 52) which is representative of increased supra-spinal neural drive.

Recent studies suggest that fatigue development may be related, at least in part, with nociception (54), and it may play a role in exercise tolerance (1). During exercise, ascending group III and IV muscle afferents discharge in response to noxious, metabolic and mechanical stimuli within the contracting skeletal muscles to regulate nociception, muscle activation and peripheral fatigue development (55, 56). As exercise-induced nociception is present in nearly all forms of time-dependent competition, the requirement for understanding its influence on performance and how athletes respond to its presence is imperative (1). Thus, the ability of an athlete to tolerate exercise-induced nociception is a critical factor in successful sports performance (54). If neuromuscular signals are consciously interpreted as nociceptive, leading to adjustments in pace or intensity, then individuals with heightened pain tolerance may be able to generate higher levels of muscle power (1). If nociception acts as a moderator of “allowed” exercise intensity, then the mechanisms that affect the level of pain tolerance may theoretically enhance performance by enabling an athlete to exercise beyond the normal protective threshold (eliciting a greater metabolic stress) (57).

The most common methods to examine the effects of group III and IV afferents is to maintain ischemia after a fatiguing contraction or trough intramuscular injection of a hypertonic saline solution (58). Recently, Norbury et al. (2021) (59) observed that induced muscle pain by hypertonic saline solution injection reduces endurance exercise performance through the exacerbation of neuromuscular fatigue, which origins in inhibitory feedback from group III/IV nociceptors, reducing central motor output. Muscle afferents adjust the motoneuronal responses induced by the stimulation at the cervicomedullary level (corticospinal pathway) during exhaustive contraction. Such motoneuronal activation might be affected rather by changes in the corticospinal excitability, altering the effectiveness of the motor unit recruitment as indicated by the amplitude of cervicomedullary motor evoked potentials (CMEPs) or thoracic motor evoked potentials (TMEPs) measured through transcranial magnetic stimulation (TMS) (60). For the upper-limbs, Martin et al., (2006) (61) verify that after 2-min MVC of the homonymous or antagonists muscles the decrease of the CMEPs on elbow extensors was maintained post contraction by holding the muscle ischemic with a cuff inflated, and this was attributed to the maintained discharge of group III and IV afferents. Despite this, the same effect was not observed for the elbow flexors muscles (62, 61). For the lower-limbs, surprisingly, Kennedy et al., (2016) (63) showed that maintaining fire of group III and IV afferents with ischemia post 2 min MVC of the homonymous or antagonists' muscles had no effect on knee extensors TMEPs. Unlike CMPEs or TMEPs pathway, H-reflex, apart from motoneuronal excitability, is also influenced and allows to assess pre and pos synaptic inhibition mechanisms (60). It was observed that H-reflex amplitude diminishes during sustained submaximal contractions at 25% and 50% MVC of the abductor pollicis brevis muscle (64). Also, H-reflex amplitude evoked in the wrist flexor muscles is reduced by metabosensitive group III and IV afferents activation, trough hypertonic saline solution injection, suggesting that the spinal motor reflex activity seems to be uniformly affected by inputs from these afferents (65). Not only the evidence is somewhat conflicting regarding the TMS research, it is important to note that in the H-reflex above-mentioned studies (64, 65), the effects of induced muscle fatigue

or pain were explored without constructing full recruitment curves individually at each time point. Instead, H reflex was obtained at single current intensities compatible with a given %Mmax. Interpretations based on this approach are seriously limited, because it does not allow determining whether the pre-selected current intensity induces a response falling in the ascending part of the recruitment curve, relevant for motoneuronal sensibility assessment.

Furthermore, to our knowledge, research that reported increases in nociception tolerance after long-term training also observed improvements in performance at post-training time point (i.e. VO₂max) (38). Unfortunately, the relationship between improved exercise performance and EIH was not explored. Moreover, since training modulates the amplitudes of evoked H and V-wave potentials (51, 52, 53), it is important to examine whether the interaction between EHI and enhanced exercise performance originates at the spinal or supraspinal level. Ultimately, the training-induced analgesic effect might enhance H-reflex and V-wave excitability, leading to an improvement in motor performance.

1.3 Purpose

Since pre and pos synaptic inhibition of group Ia afferents can both be affected by metaboreflex activation (66), explaining H-reflex inhibition under these conditions, further research is needed to explore whether analgesic effects of post-acute and chronic exercise are partially dependent on lower H-reflex inhibition by group III and IV muscle afferents desensitization. In addition, it is important to note that the available research examining the interaction between exercise (acute and chronic) and nociception did not compare the effect of different exercise modalities. Since discharge rate of III and IV afferents is highly dependent on specific task-metabolic requirements (67), it is relevant to determine if exercise modality differentially modulates the possible analgesic response via metaboreflex desensitization (acute and chronic desensitization).

Therefore, with this project, we aim at exploring the influence of experimentally induced metaboreflex activation (group III and IV afferents) (maintained submaximal

isometric contraction followed by blood-flow occlusion) Vs. a control condition (no isometric contraction nor blood flow occlusion), on H-reflex recruitment curve and V wave excitability (aim #1). Since the activation of group III/IV afferents can inhibit the corticospinal pathway (61) we hypothesize that the normalized maximal amplitude and the slope of the ascending limb of the H-recruitment curve will decrease with metaboreflex activation. Additionally, we intend to examine the acute impact of different exercise modalities (resistance, supramaximal and endurance) on nociception sensibility (by the application of a cold tolerance test and by determining pressure pain threshold) (aim #2). This will allow us to investigate the role of different acute exercise paradigms on possible metaboreflex desensitization in its relationship with altered neuromuscular responses at post-exercise time point (attenuated inhibition of H-reflex and V-wave amplitude during metaboreflex activation). Also, once past research has shown that muscle metaboreflex activation reduces the sensitivity of the baroreflex (68), we will measure arterial pressure (AP) and heart rate variability (HRV) during cold pain tolerance testing. Despite all exercise modalities could enhance reducing pain sensibility after exercise, we hypothesize that resistance and supramaximal exercise stimuli will enhance nociceptive tolerance via metaboreflex desensitization compared to that seen with endurance exercise (attenuated increase of AP and sympathetic component of HRV during cold pressor test). Finally, we intend to explore the impact of long-term resistance, supramaximal and endurance training on nociceptive sensibility, using the same tests of aim #2 (aim #3). We hypothesize that chronic EIH will be of greater magnitude after supramaximal and resistance exercise training vs. endurance training. In addition, we hypothesize that decreased nociception will be related with attenuated inhibition of H-reflex and V-wave amplitude and attenuated increase of AP and sympathetic component of HRV during metaboreflex activation after training and this will result in increased exercise performance via heightened H-reflex and V-wave excitability.

2. Research Plan and Methods

2.1 Aim #1

2.1.1 Participants

We will recruit a total of 16 participants ((G Power 3.0.10 software) to achieve 80% of correctly reject the null hypothesis, based on Duchateau et al., (2002) (64)). Specific inclusion and exclusion criteria are discussed in subsection 2.4.1

2.1.2 Study design

To study the influence of experimentally induced metaboreflex activation on H-reflex and V-wave excitability, participants will be tested on 2 different conditions (with and without maintained submaximal isometric contraction followed by blood flow occlusion, using a randomized, crossover approach). The experimental design is illustrated in figure 1.

2.2 Aim #2

2.2.1 Participants

The intervention study will enroll 24 participants ((G Power 3.0.10 software) to achieve 80% of correctly rejecting the null hypothesis, based on Jones et al., (2016) (11)). Eight participants will be randomly allocated to each exercise modality (i.e. resistance, supramaximal and endurance). Specific inclusion and exclusion criteria are discussed in subsection 2.4.1.

2.2.2 Study design

In a randomized and crossover trial, on 2 different days, participants will be tested before and after performing acute bouts of different exercise modalities or

passive rest. Participants will be tested for: (1) pressure pain threshold, (2) cold pain tolerance with concomitant measures of AP and HRV, (3) the influence of metaboreflex activation (maintained submaximal isometric contraction followed by blood flow occlusion) on H-reflex and V-wave excitability. For those enrolled in endurance and resistance exercise modalities, participants will visit the laboratory on a previous day for $VO_{2\text{max}}$ and maximal repetition assessments for rigorous exercise prescription on experimental day. The experimental design is illustrated in figure 2.

2.2.3 Exercise protocols

Participants allocated to resistance exercise will perform 3 sets of 2 bilateral leg exercises (leg press and seated calf raise). The load intensity will be set at 8-12 maximal repetitions. Participants allocated to endurance exercise will perform 30 min on the speed compatible with 75% of $VO_{2\text{max}}$. Participants allocated to supramaximal exercise will perform 2 bouts of 30 s of supramaximal cycling exercise, using a relative load equivalent to 7.5% of the individual body mass (MonarkErgomedic 894E®). Both bouts of supramaximal exercise will be interspersed with 4 min of active recovery.

2.3 Aim #3

2.3.1 Participants

We will recruit a total of 30 participants. Sample size is overestimated in order to allow us to accommodate an attrition rate of ~ 20% during follow up, once participants will only be eligible for final testing if they attain at least 85% of the training sessions, with the goal of allocating at least 8 participants to each of the three training groups (G Power 3.0.10 software; to achieve 80% of correctly reject the null hypothesis, based on Jones et al. 2014 (38)). Specific inclusion and exclusion criteria are discussed in

subsection 2.4.1

2.3.2 Study design

Each intervention group will perform 6 weeks of exercise training (resistance, supramaximal and endurance training). Participants allocated to each training group will be evaluated before and after training. On one day participants will be tested for pressure pain threshold and cold pain tolerance with concomitant measures of AP and HRV. The influence of metaboreflex activation (maintained submaximal isometric contraction followed by blood flow occlusion) on H-reflex and V-wave parameters will also be measured. On another day, participants will be evaluated for resting AP and HRV, neuromuscular adaptations and performance. The experimental design is illustrated in figure 3.

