2.4.13 Statistical analysis (aim #1, #2 and #3)

Normality will be verified through the Shapiro-Wilk test. Univariate ANOVAs will be used to explore differences in the impact of blood-flow occlusion vs. non-blood flow occlusion on each H-reflex and V-wave variable (aim #1). Repeated measures ANOVA will be computed to determine significant main effects for time (pre- vs. post-acute exercise), condition (resistance vs. supramaximal vs. endurance exercise) and time-by-condition interactions on pain tolerance/threshold/ratings, AP, HRV and H-

reflex parameters and V-wave amplitude with metaboreflex activation (aim #2). Repeated measures ANOVA will be computed to determine significant main effects for time (pre- vs. post training), condition (resistance vs. supramaximal vs. endurance training) and time-by-condition interactions on exercise performance, pain tolerance/threshold/ratings, AP, HRV, H-reflex parameters and V-wave amplitude with metaboreflex activation, and neuromuscular adaptations to training (aim #3). Correlations between the impact of exercise or training on pain tolerance/threshold/ratings and performance on H-reflex, V-wave, AP and HRV variables will also be explored. Significance level will be set at $p < 0.05$. All data will be treated using SPSS 25.0 for statistical analysis.

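### Aim #3 does not state random allocation in its readable text, and its time-by-condition test compares raw change without using the measured baseline

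*Combined protocol and SAP*

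**What the plan says.** **Allocation.** Section 2.1.2 describes Aim #1 as a randomised crossover. Section 2.2.1 says of Aim #2: "Eight participants will be randomly allocated to each exercise modality". For Aim #3, section 2.3.1 plans recruitment "with the goal of allocating at least 8 participants to each of the three training groups", and section 2.3.2 says "Participants allocated to each training group will be evaluated before and after training". The readable text of 2.3.1 to 2.3.3 gives no random sequence or concealment. Section 2.3.2 refers to Figure 3 for the design, and that figure is not shown.

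**Hypothesis.** Section 1.3 is directional: a larger chronic hypoalgesic effect after supramaximal and resistance training than after endurance training.

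**Analysis.** Section 2.4.13 specifies repeated-measures ANOVA with time (before, after training), "condition (resistance vs. supramaximal vs. endurance training) and time-by-condition interactions on exercise performance" and the other outcomes. It names no baseline covariate.

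**Numbers and follow-up.** "We will recruit a total of 30 participants", to allow for "an attrition rate of ~ 20% during follow up"; "participants will only be eligible for final testing if they attain at least 85% of the training sessions" (2.3.1).

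**Performance.** Sections 2.3.4.1 to 2.3.4.3 give each group its own test: knee-extension strength and endurance, a treadmill run, or repeated 30 s cycling sprints.

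**The concern.** Aim #3 compares training modalities between separate groups of about eight men each, so the comparison depends on how men enter the groups. Recruitment is by word of mouth among recreationally active men (2.4.1). Nothing in the readable text rules out entry by preference or fitness, and a missing randomisation cannot be repaired after the trial.

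The analysis raises a second matter even if allocation is random. Groups this small will often differ at baseline by chance. A comparison of raw change carries part of that difference into the result, because higher starting values tend to fall back. The baseline is measured anyway, and using it as a covariate would correct for this and usually sharpen the estimate.

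**Working it through.** **1. The plan's own figure.** Three groups of 8 give 24. With 20% attrition, 24 / (1 − 0.20) = 30, as stated. The 80% power behind 8 per group cannot be checked, because no effect size, SD, pre-post correlation or test is given. The correlation ρ below is therefore assumed.

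**2. What the planned test is.** With two time points and one between-group factor, the time-by-condition F test is identical to a one-way ANOVA on post minus pre, with 2 and 21 degrees of freedom at 3 × 8.

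**3. Chance imbalance under perfect randomisation.** For two groups of n, the baseline difference has standard deviation √(2/n) in SD units, and P(|difference| > 0.5 SD) = 2[1 − Φ(0.5/√(2/n))].
- n = 8: 0.5/0.5 = 1.00, probability 32%.
- n = 10: 0.5/0.447 = 1.12, probability 26%.
- Largest of the three pairwise gaps at n = 8, by simulation: above 0.5 SD in 58% of trials and above 1 SD in 11%.

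Given such a gap, the expected shift in the change-score difference is (1 − ρ) times the gap. For 0.5 SD that is 0.25 SD at ρ = 0.5 and 0.10 SD at ρ = 0.8.

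**4. Precision.** In units of the outcome variance, a change score has variance 2(1 − ρ) and an ANCOVA residual has 1 − ρ². Their ratio is (1 + ρ)/2. Estimating the slope costs one degree of freedom and inflates the variance by about 1 + 1/19 = 20/19.

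**5. Power of the three-group test.** 80% power at 2 and 21 df needs a noncentrality of 11.15. For ANCOVA, divide this by the ratio after slope cost and use 2 and 20 df.

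| Assumed ρ | (1+ρ)/2 | After slope cost | Noncentrality | ANCOVA power |
|---|---|---|---|---|
| 0.5 | 0.75 | 0.789 | 14.13 | 88.6% |
| 0.7 | 0.85 | 0.895 | 12.46 | 84.2% |
| 0.8 | 0.90 | 0.947 | 11.77 | 81.9% |
| 0.9 | 0.95 | 1.000 | 11.15 | 79.7% |

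**6. The directional hypothesis as one contrast.** This test is not in the plan; it is shown for scale. The mean of resistance and supramaximal minus endurance, at 8 per group, has variance factor (1/4)(1/8 + 1/8) + 1/8 = 3/16. For an assumed 0.8 SD difference, two-sided 5%, power moves from 42% to 51% (ρ = 0.5), 62% to 67% (0.7) and 80% to 81% (0.8) after the slope cost.

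**The case against.** **Randomisation may be intended.** Section 2.2.3 uses the bare word allocated for Aim #2 groups that section 2.2.1 has already said are random. The text surviving beside Figure 1 carries a randomisation label, so Figure 3 may do so too. This stands. A reader might infer that men choose their modality, but no section describes choice or fitness-based entry. What the documents support is that the readable text does not state the method.

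**Under randomisation the planned test is valid.** This also stands. Change scores are then unbiased on average, so the case for ANCOVA is precision and correction of chance imbalance. At ρ = 0.9 there is no gain.

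**ANCOVA does not rescue non-random groups.** A reader might infer that baseline adjustment removes selection bias. Simulations of 3 × 8 with no training effect show that the answer depends on the model. If one group starts 1 SD higher and regresses to a common mean, the change-score test rejects in 14.7% of trials at ρ = 0.5 and ANCOVA in about 5%. If the 1 SD difference is stable, change scores stay near 5% and ANCOVA rejects in roughly 15 to 16%. Randomisation is what protects here; adjustment is no substitute.

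**Allocation cannot simply follow all baseline testing.** Baseline performance tests depend on the group (2.3.4.1 to 2.3.4.3), so randomising after all of them would mean giving every man all three. Nor can one ANCOVA cover an outcome that is a different variable in each group. Both points stand and shape the fix.

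**Conclusion.** The point holds as a gap in the text and a low-cost improvement in the analysis. The readable Aim #3 text does not state random allocation, unlike Aim #2, and the planned between-modality test ignores the measured baseline.

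If the planned test has 80% power at 3 × 8, baseline adjustment gives about 89% at ρ = 0.5 and nothing extra at ρ = 0.9. These figures assume random allocation, a linear relation with a common slope, 24 men analysed and a correlation the documents do not give.

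It would go too far to say that the two changes remove selection and imbalance at no cost. Randomisation prevents systematic selection at entry but leaves chance imbalance. ANCOVA handles only the measured baseline of the outcome and spends one degree of freedom. Neither addresses selection after allocation: final testing is limited to men who attended at least 85% of sessions.

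**What to change.** **Section 2.3.2.** State that the 30 participants are randomised 10:10:10 in permuted blocks with a concealed sequence. Open the allocation after the common pain, AP/HRV and neuromuscular baseline, but before the modality-specific performance tests. Section 2.3.2 puts resting AP/HRV, neuromuscular testing and performance on the same day, and the endurance group also needs a ramp test on a different day from its time trial. The order of these steps should therefore be written out. If Figure 3 already states randomisation, bring the text into line with it.

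**Section 2.4.13.** For outcomes measured identically in all three groups, replace the Aim #3 time-by-condition test with ANCOVA: post-training value as outcome, modality as factor and the same variable's pre-training value as covariate. Leave exercise performance out of this between-modality analysis.

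**Cost.** A randomisation list, a means of concealment, protocol and SAP wording, and one degree of freedom. The sample size stays at 30.
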